# 1.3.2 Schedule of Activities: Treatment Period and Follow-up

## 1.3.2.1 Part A Schedule of Activities: Treatment Period and Follow-up

Table 4 Schedule of Activities for Part A: Treatment Period and Follow-up

	Treatment Period											
Week	0	4	8	12	16	20	24	32	40	48		Follow-up
Visit	V2	V3	V4	V5	V6	V7	V8	V9	V10	V11 (EOT)	E/D Visit b	4 weeks after EOT or E/D (± 5d) a
Day (visit window ± x days) a	1	29 ± 5d	57 ± 5d	85 ± 5d	113 ± 5d	141 ± 5d	169 ± 5d	225 ± 5d	281 ± 5d	337 ± 5d		
Confirmation of fasting (Section 5.3.2)	X									X	X	
Demonstration of and training on self- administration of SC injection (Section 6.2) °	X											
Review of adherence to diet and lifestyle advice (Section 5.3.1)	X	X	X	X	X	X	X	X	X	X	X	X
Concomitant medication (Section 6.5)	X	X	X	X	X	X	X	X	X	X	X	X
12-lead dECG (Section 8.2.4) d	X	X	X	X	X	X	X	X	X	X	X	X
Vital signs (Section 8.2.3) e	X f	X	X	X	X	X	X	X	X	X	X	X
Abbreviated (symptom-directed) physical examination including weight (Section 8.2.2, Section 8.1.4)	X	X	X	X	X	X	X	X	X	X	X	X
Assessment of AEs and injection site reactions (Section 8.3; Section 8.2.6.1) g, h	X	X	X	X	X	X	X	X	X	X	X	X
Clinical safety laboratory assessments, including eGFR and MELD score calculation (Section 8.2.5)	X	X	X	X	X	X	X	X		X	X	X
Amylase and lipase (Section 8.2.5)	X						X	X		X	X	X
Coagulation parameters (Section 8.2.5)	X						X	X		X	X	X
Calcitonin (Section 8.2.5)	X									X	X	

Table 4 Schedule of Activities for Part A: Treatment Period and Follow-up

	Treatment Period											
Week	0	4	8	12	16	20	24	32	40	48		Follow-up
Visit	V2	V3	V4	V5	V6	V7	V8	V9	V10	V11 (EOT)	E/D Visit b	4 weeks after EOT or E/D (± 5d) a
Day (visit window ± x days) a	1	29 ± 5d	57 ± 5d	85 ± 5d	113 ± 5d	141 ± 5d	169 ± 5d	225 ± 5d	281 ± 5d	337 ± 5d		
Urine pregnancy test (WOCBP only) (Section 8.2.5)	X			X			X			X	X	X
Liver biopsy for histology (Section 8.1.1)										X i	X j	
FibroScan, LSM, CAP, FAST Score, Agile 3+ (Section 8.1.3) k,1	X									X	X	
Randomization in IRT/RTSM (Section 6.3)	X											
Study intervention administration in clinic m	X	X	X	X	X	X	X	X	X			
Study intervention dispensed for at home administration	X	X	X	X	X	X	X	X	X			
Instructions for use dispensed	X	X	X	X	X	X	X	X	X			
Uptitration step for 300 µg cotadutide/placebo		X	X	X								
Uptitration step for 600 µg cotadutide/placebo		X	X	X	X	X	X					
Study intervention compliance (Section 6.4)		X	X	X	X	X	X	X	X	X	X	

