## 3.3.2 Visit Window

For the purpose of the statistical analysis, study findings are allocated to the analysis visit using analysis visit windows as described in Table 2, Table 3, Table 4, Table 5, Table 6, Table 7, and Table 8. Note, study day 1 refers to the date the participant received the first dose of IP.

Table 2 Analysis Visit Windows, Biopsy

Analysis Visit	Target Day	Day Range
Week 48	337	1 through end of study

Table 3 Analysis Visit Definitions, 12-lead dECG, Vital Signs, Abbreviated Physical Examination

Analysis Visit	Target Day	Day Range
Week 4	29	2-42
Week 8	57	43-70
Week 12	85	71-98
Week 16	113	99-126
Week 20	141	127-154
Week 24	169	155-196
Week 32	225	197-252
Week 40	281	253-308
Week 48	337	309-351
Week 52	365	352-385

dECG, digital electrocardiogram.

Table 4 Analysis Visit Definitions, Clinical Laboratory Assessments Including eGFR and MELD but Excluding Fasting Glucose (Safety)

Analysis Visit	Target Day	Day Range
Week 4	29	2-42
Week 8	57	43-70
Week 12	85	71-98
Week 16	113	99-126
Week 20	141	127-154
Week 24	169	155-196
Week 32	225	197-280

Table 4 Analysis Visit Definitions, Clinical Laboratory Assessments Including eGFR and MELD but Excluding Fasting Glucose (Safety)

Analysis Visit	Target Day	Day Range
Week 48	337	281-351
Week 52	365	352-385

Due to fasting at the Week 48 visit, random glucose will not be presented for the Week 48 analysis visit. eGFR, estimated glomerular filtration rate; MELD, model for end-stage liver disease.

Table 5 Analysis Visit Definitions, Amylase, Lipase, Coagulation

Analysis Visit	Target Day	Day Range
Week 24	169	2-196
Week 32	225	197-280
Week 48	337	281-378

Table 6 Analysis Visit Definitions, Calcitonin, FibroScan, FAST, Agile 3+, BARD, Fasting Serum Lipid Panel, ELF, Pro-C3, FIB-4, Fasting Plasma Glucose (Efficacy), Fasting Glucose (Safety), C-peptide, Adiponectin

Analysis Visit	Target Day	Day Range
Week 48	337	2-378

BARD, BMI, AST/ALT ratio, diabetes; ELF, enhanced liver fibrosis; FAST, FibroScan-ALT; FIB-4, fibrosis-4; Pro-C3, released N-terminal propeptide of type III collagen.

Table 7 Analysis Visit Definitions, PK, and ADA

Analysis Visit	Target Day	Day Range
Week 4	29	2-57
Week 12	85	58-127
Week 24	169	128-253
Week 48	337	254-378

ADA, anti-drug antibody; PK, pharmacokinetic(s).

Table 8 Analysis Visit Definitions, HbA1c, Urine Albumin, Creatinine

Analysis Visit	Target Day	Day Range
Week 12	85	2-127
Week 24	169	128-253
Week 48	337	254-378

HbA1c, hemoglobin A1c.

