## 4.2.3 Other Endpoints

#### 4.2.3.1 Definition

Tertiary/exploratory endpoints will be tested versus placebo at the 2-sided nominal alpha 5% level, without consideration of multiplicity:

The following are histological endpoints, to be assessed centrally 1) by independent pathologists and 2) by artificial intelligence, as detailed in the Central Histopathology Review

Charter. Analysis of continuous histological scores, if included, will be based solely on values provided by artificial intelligence.

- Proportion of participants with resolution of NASH without worsening of liver fibrosis based on biopsy at Week 48
- Proportion of participants with improvement of liver fibrosis by at least 1 stage without worsening of NASH based on biopsy at Week 48. (Worsening of NASH is defined as any increase in the ballooning, inflammation, or steatosis scores even if total NAS does not increase.)
- Proportion of participants with both resolution of NASH and improvement in fibrosis by at least 1 stage based on biopsy at Week 48
- Proportion of participants with improvement in fibrosis by at least 1 stage based on biopsy at Week 48
- Proportion of participants with improvement in NAS based on biopsy at Week 48
- Change from baseline in NAS based on biopsy at Week 48
- Change from baseline in fibrosis stage based on biopsy at Week 48
- Proportion of participants with progression, no change, or regression in fibrosis stage based on biopsy at Week 48
- Proportion of participants with improvement in key histological features of NASH on biopsy at Week 48, including:
  - Inflammation
  - Steatosis
  - Ballooning

Below are other exploratory/tertiary endpoints not based on biopsy:

- Change from baseline in liver enzymes including ALT and AST through Week 48
- Change from baseline in triglycerides, LDL cholesterol, and HDL cholesterol, non-HDL cholesterol, and total cholesterol, and HbA1c through Week 48
- Cotadutide PK exposure will be summarized and compared with prior data for consistency
- Change from baseline at Week 48 in:
  - LSM as assessed by FibroScan
  - Percentage CAP as assessed by FibroScan
- Changes from baseline at Week 48 in non-invasive disease-specific biomarkers, including but not limited to:
  - Pro-C3

- ELF score
- FIB-4
- APRI
- NFS
- BARD score
- FAST score
- Agile 3+
- Percent change from baseline in body weight at Week 48
- Change from baseline in FPG, adiponectin, and C-peptide at Week 48

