# 4.2.3.3 Handling of Dropouts and Missing Data

A post-baseline liver biopsy is planned for each participant at Week 48. Participants who discontinue study intervention early will have an early discontinuation visit. Participants will be encouraged to have the biopsy at Week 48 as planned in the CSP schedule of activities. Participants who are unwilling or unable to wait until Week 48 will have the biopsy procedure as part of the early discontinuation visit if they have received study intervention for at least 36 weeks. Participants who have not been on study intervention for at least 36 weeks will not have a biopsy at the early discontinuation visit.

Unless stated otherwise, the following rules will be used for missing data in exploratory endpoints:

- For biopsy endpoints analysis using the FAS analysis set, will impute missing observations as non-responders while analysis using the PP analysis set will exclude participants with missing data.
- Missing observations for ordinal endpoints will not be imputed, unless otherwise stated.
- Missing observations for continuous endpoints for analyses including multiple postbaseline timepoints will not be imputed.
- Missing observations for continuous endpoints for analyses including only a single post-baseline timepoint will be imputed using multiple imputation (monotone regression) separately by randomized treatment arm with stratification variables (baseline fibrosis stage and T2DM status) and baseline measurement for the endpoint as independent variables. If an issue is encountered for fitting an imputation model (eg, collinearity with intercept), a simplified imputation model may be used.

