## 4.2.3.4 Primary Analysis of Other Endpoints

Unless otherwise indicated, analyses of tertiary/exploratory histological endpoints and continuous exploratory endpoints at Week 48 will include both on- and off-treatment measurements while analyses of endpoints at multiple timepoints through Week 48 will only include on-treatment measurements. The treatment effect for binary exploratory endpoints will be analyzed by the Cochran-Mantel-Haenszel (CMH) test, stratified for T2DM presence and F2/F3 fibrosis stages. The difference in proportion (unstratified response difference) with Miettinen-Nurminen (ie, score-based; without stratification) 95% confidence interval, and nominal p-value from CMH chi-square test will be provided.

Continuous endpoints summarized for a single post-baseline timepoint (Week 48) will be analyzed using ANCOVA with baseline, baseline T2DM status, baseline fibrosis stage, and treatment as independent variables, using multiple imputation. If an issue is encountered for fitting an ANCOVA model (eg, collinearity with intercept), a simplified model may be used. For analysis of (absolute) change from baseline, endpoints will be analyzed without transformation and LSMEAN change from baseline by treatment; the treatment effect as the LSMD will be reported as point estimates and 95% confidence intervals with p-values provided for treatment effect. For analysis of percent change from baseline, ANCOVA will be performed using log-transformed values. Point estimates and 95% confidence intervals of percent change from baseline by treatment and ratio change from baseline will be reported with a nominal p-value for treatment effect (Section 4.2.3.2). Rubin's rules (Rubin 1987) will be used to pool LSMEAN and LSMD values and associated standard errors across multiply imputed datasets and will provide the reported estimates and p-values. The following variables will be log-transformed: ALT, AST, APRI, triglycerides, PRO-C3, FIB-4, FPG, (total and high molecular weight) adiponectin, and C-peptide. Other variables may be log-transformed if required.

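### The imputation of missing Week 48 body weight ignores the weights scheduled at eight earlier visits; the cost is modest and easily avoided

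*SAP*

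**What the plan says.** The endpoint in SAP 4.2.3.1 is "Percent change from baseline in body weight at Week 48", a single post-baseline timepoint. Under SAP 4.2.3.4, "Continuous endpoints summarized for a single post-baseline timepoint (Week 48) will be analyzed using ANCOVA". Under SAP 4.2.3.3 a missing value is "imputed using multiple imputation (monotone regression) separately by randomized treatment arm", and the predictors are "stratification variables (baseline fibrosis stage and T2DM status) and baseline measurement for the endpoint as independent variables". No post-baseline value is among them. Protocol 9.4.2 asks only for multiple imputation and names no predictors.

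In the Protocol 1.3.2.1 schedule (Table 4), the row "Abbreviated (symptom-directed) physical examination including weight" is marked at Weeks 0, 4, 8, 12, 16, 20, 24, 32, 40 and 48, at the early-discontinuation (E/D) visit and at follow-up. That gives eight post-baseline weights before Week 48.

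No SAP window table names body weight. Because the schedule places weight within the abbreviated examination, I read it as governed by SAP Table 3, "Analysis Visit Definitions, 12-lead dECG, Vital Signs, Abbreviated Physical Examination". That table has a window for each of these weeks and sets Week 48 at Days 309–351. SAP 4.2.3.4 adds that analyses of "continuous exploratory endpoints at Week 48 will include both on- and off-treatment measurements".

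The repeated-measures model (MMRM) in SAP 4.2.3.4 is for endpoints followed through Week 48, and weight is not listed as one. SAP 4.2.3.5 plans no additional analyses.

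**The concern.** The single-timepoint rule suits markers such as Pro-C3 or C-peptide. These have no scheduled post-baseline value between baseline and Week 48 other than at E/D, and their Week 48 window (SAP Table 6, Days 2–378) takes in the E/D value. Weight is different. It is followed at nearly every visit, and its Week 48 window is narrow. A participant with no weight in that window is imputed from baseline and strata, even if the file holds months of weights.

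Two things follow. Recorded weights that predict the missing one are unused, which costs precision in a trial of about 55 participants. The imputation also treats leavers as comparable, within arm and given baseline and strata, with those who stayed. If leaving is related to the weight change so far, and differently by arm, the treatment contrast is biased. Different leaving by arm is plausible, because Protocol 2.2.2 reports more nausea and vomiting on cotadutide than on placebo. At stake is the Week 48 weight contrast, for which Protocol Table 8 sets an exploratory superiority objective.

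**Working it through.** **1. The plan's own figure.** The documents give no calculation for weight. Their one computed figure is the original Part A power (Protocol 9.2: 100 versus 100, 15% versus 35%, two-sided 0.05, power above 90%). With pooled null variance, (0.2 − 1.96 × √(2 × 0.25 × 0.75/100)) / √((0.15 × 0.85 + 0.35 × 0.65)/100) = 1.342, so power is 91.0%. It reproduces, and this point does not depend on it.

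**2. Who is affected.** Protocol Table 4 sets follow-up at E/D + 28 ± 5 days.
- E/D on Days 309–351: the E/D weight is itself in the Week 48 window.
- E/D on Days 286–308: follow-up falls between Day 286 + 23 = 309 and Day 308 + 33 = 341, always inside the window.
- E/D on Days 276–285: it depends on the follow-up date. From Day 281, an on-time follow-up falls on Day 309.
- E/D on Day 275 or earlier: the latest follow-up is Day 308, so there is no Week 48 weight unless the participant continues with visits.

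The imputed group is therefore those who leave before about Day 276, plus those who miss the later visits.

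**3. Precision, large-sample formula.** Suppose a fraction d is missing at random and an earlier weight, with correlation ρ to Week 48, is available for everyone. Then the SE with that weight divided by the SE without it is √{(1−d)[ρ² + (1−ρ²)/(1−d)]} = √(1 − ρ²d). Reduction in SE:

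| ρ | d = 10% | 20% | 30% |
|---|---|---|---|
| 0.70 | 2.5% | 5.0% | 7.6% |
| 0.80 | 3.3% | 6.6% | 10.1% |
| 0.90 | 4.1% | 8.5% | 13.0% |
| 0.95 | 4.6% | 9.5% | 14.6% |

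**4. Simulation.** Assumed, none from the documents:
- SD of percent change 6 points at Week 48;
- correlation with Week 48 of 0.91 for Week 40 and 0.71 for Week 24;
- mean change −1% on placebo and −6% on active, so a true effect of −5 points;
- dropout of about 10, 20 or 30%, random or driven by the last observed change.

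From 55 participants at 2:1:2:1 the groups are about 18, 9, 18 and 9; pooling placebo gives 18 versus 18. The SAP model (baseline and strata) was compared with sequential regression that adds the preceding weight.

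SD of the estimated effect, 18 per arm, 1,200 trials, 10 imputations (SAP model → with preceding weight):

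| Dropout | 10% | 20% | 30% |
|---|---|---|---|
| Random | 2.23 → 2.18 (2.6%) | 2.48 → 2.35 (4.9%) | 2.90 → 2.64 (9.1%) |
| Poor responders, same threshold in both arms | 2.26 → 2.24 (1.0%) | 2.46 → 2.43 (1.1%) | 2.61 → 2.58 (1.1%) |
| Poor responders, active arm only | 2.21 → 2.12 (4.1%) | 2.47 → 2.36 (4.6%) | 2.89 → 2.63 (9.1%) |

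Excess bias of the SAP model over complete data, in points, 3,000 per arm (positive is toward no effect):

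| Dropout | 10% | 20% | 30% |
|---|---|---|---|
| Same threshold in both arms | +0.16 | +0.27 | +0.45 |
| Active arm only | −0.25 | −0.51 | −0.73 |
| Each arm loses its own worst responders | +0.04 | +0.01 | +0.04 |

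With the preceding weight added, excess bias is within 0.04 points throughout. At 18 per arm the SAP model gives +0.11, +0.26 and +0.40 in the first row and −0.21, −0.45 and −0.69 in the second; with the preceding weight it is within 0.06. The Monte Carlo SE of a mean at 18 per arm is about 2.5/√1200 = 0.07.

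**5. Sensitivity to visit noise.** In smaller simulations (250–300 trials, SD 6, 24%/19% missing at random), visit noise of 0.8 points gave SE reductions of 13% (2.45 → 2.14) and 16% (2.69 → 2.26). Noise of 2 points gave 4% (2.78 → 2.68).

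**6. Scale.** The simulations use percentage points, while the SAP analyses the log ratio. At these sizes the two nearly agree: ln(0.94) = −0.062.

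**The case against.** The strongest reply is that little turns on this. Weight is one of many exploratory endpoints, p-values are nominal, safety is primary, development has stopped, and the plan complies with the protocol. All of that stands. It limits the priority of the point but gives no reason to leave recorded weights out.

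The affected group may also be small. Protocol 7.1 encourages participants who stop treatment to stay for the remaining visits, and their off-treatment Week 48 weight is used. A reader might infer that someone who leaves at Week 40 is imputed as though nothing were known after Day 1. Step 2 shows otherwise: an on-time follow-up weight from Day 281 onward is an observed Week 48 value.

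Two further readings are tempting and not supported. The first is that the plan wastes the equivalent of about 31% more participants. That is the 2.45 → 2.14 case (variance ratio 0.763; 1/0.763 = 1.31), and it needs visit noise of 0.8 points against a person SD of 6, which makes trajectories almost deterministic. The second is that the plan exaggerates the drug effect. It does so if poor responders leave mainly the active arm. Under a common threshold the bias goes the other way, and gastrointestinal intolerance need not select poor responders at all.

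The objection with most force concerns small groups. Imputation is by randomized arm, and the SAP does not say whether the two placebo groups are pooled for it. With placebo kept as 9 + 9 and 20% dropout, sequential regression could not be fitted in 24–28% of simulated trials, against 14–17% for the planned model. Its median SE worsened under random-walk trajectories (2.94 → 3.28), though it improved under low visit noise (3.07 → 2.66). This stands, and it shapes the fix.

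**Conclusion.** The point holds as a modest improvement to a stated rule. The text is clear that the imputation model has no post-baseline predictor, that eight earlier weights are scheduled, and that no planned efficacy analysis of weight uses them. The size is less certain, because SD, correlations and dropout are all assumed. Across the ranges shown, the preceding weight saves roughly 1–15% of the SE. It removes most of a bias of roughly 0.2–0.7 points on a 5-point effect when dropout depends on earlier weight differently by arm. The documents do not allow the direction of that bias to be predicted, and under random or symmetric loss it is about zero. Only participants with no weight in Days 309–351 contribute, and no primary safety conclusion changes.

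**What to change.** Add a body-weight exception to SAP 4.2.3.3:
- Impute weight by sequential monotone regression in visit order, using the preceding visit's weight with baseline weight, fibrosis stage and T2DM status. One or two key visits, such as Weeks 24 and 40, would serve instead.
- Use both on- and off-treatment weights.
- Pool the two placebo groups for this imputation, and say so.
- State how intermittent gaps are filled, since monotone regression needs a monotone pattern.
- Keep the existing simplified-model fallback and the Week 48 ANCOVA contrast.

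Do not enter all eight weights at once. With intercept, baseline and two strata that makes 4 + 8 = 12 coefficients, against about 18 participants per dose. Adding only the preceding weight makes 5.

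The cost is a few sentences in the SAP, slightly more programming and one more predictor in small groups. No new data are needed, and Protocol 9.4.2 is still followed. If the data are already unblinded, report this as a labelled sensitivity analysis beside the planned one.

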## 4.2.3.4 Primary Analysis of Other Endpoints

Unless otherwise indicated, analyses of tertiary/exploratory histological endpoints and continuous exploratory endpoints at Week 48 will include both on- and off-treatment measurements while analyses of endpoints at multiple timepoints through Week 48 will only include on-treatment measurements. The treatment effect for binary exploratory endpoints will be analyzed by the Cochran-Mantel-Haenszel (CMH) test, stratified for T2DM presence and F2/F3 fibrosis stages. The difference in proportion (unstratified response difference) with Miettinen-Nurminen (ie, score-based; without stratification) 95% confidence interval, and nominal p-value from CMH chi-square test will be provided.

Continuous endpoints summarized for a single post-baseline timepoint (Week 48) will be analyzed using ANCOVA with baseline, baseline T2DM status, baseline fibrosis stage, and treatment as independent variables, using multiple imputation. If an issue is encountered for fitting an ANCOVA model (eg, collinearity with intercept), a simplified model may be used. For analysis of (absolute) change from baseline, endpoints will be analyzed without transformation and LSMEAN change from baseline by treatment; the treatment effect as the LSMD will be reported as point estimates and 95% confidence intervals with p-values provided for treatment effect. For analysis of percent change from baseline, ANCOVA will be performed using log-transformed values. Point estimates and 95% confidence intervals of percent change from baseline by treatment and ratio change from baseline will be reported with a nominal p-value for treatment effect (Section 4.2.3.2). Rubin's rules (Rubin 1987) will be used to pool LSMEAN and LSMD values and associated standard errors across multiply imputed datasets and will provide the reported estimates and p-values. The following variables will be log-transformed: ALT, AST, APRI, triglycerides, PRO-C3, FIB-4, FPG, (total and high molecular weight) adiponectin, and C-peptide. Other variables may be log-transformed if required.

Change from baseline in continuous fibrosis scores from artificial intelligence, if available, will be analyzed by ANCOVA, as described above. Additionally, continuous scores from artificial intelligence for key histological features of NASH (inflammation, steatosis, ballooning), if available, may be analyzed using ANCOVA. Change from baseline in fibrosis stage (non-continuous scores) based on biopsy at Week 48 will not be analyzed by ANCOVA, but will instead be summarized descriptively by treatment using shift tables.

Analysis of continuous endpoints at multiple timepoints will be performed using MMRM adjusting for baseline value, fibrosis stage (F2/F3), T2DM status, analysis visit, treatment, the interaction of treatment and analysis visit and the interaction of baseline value and analysis visit. Only on-treatment data (Section 3.3.1) will be included in the model and missing data will not be imputed. An unstructured covariance structure will be used. If the computational algorithm fails to converge, the following structures will be tested in the following order:

Toeplitz, first-order autoregressive (AR[1]), and compound symmetry. Alternatively, covariates may be dropped from the model. Estimates, standard errors, and 95% confidence intervals of mean change from baseline or percent change from baseline will be reported by treatment and analysis visit. Restricted Maximum Likelihood estimation will be used in MMRM analyses.

